3. DESCRIPTION OF DESIGN AND TRIAL POPULATION

3.1 OVERALL TRIAL DESIGN AND PLAN

This is a Phase I, non-randomized, uncontrolled, open-label, dose escalation trial of BI 836880 monotherapy and combination therapy of BI 836880 and BI 754091, which are administered intravenously every 3 weeks. The eligible patient population will be advanced solid tumours. The trial consists of two Parts; Part I (monotherapy part) and Part II (combination therapy part). Part II will commence after completion of Part I.

The data obtained from the trial will determine the MTD estimate based on a Bayesian logistic regression model with overdose control ([R13-4803](#)). The BLRM estimates the MTD by updating estimates of the probability of observing a DLT in the MTD evaluation period for each dose level in the trial as patient information becomes available. At any time in the trial, it will not be permitted to escalate to a dose which does not fulfil the escalation with overdose control (EWOC) principle (refer to Section [7](#)).

Successive cohorts of patients will receive increasing doses of BI 836880 single agent or combination of BI 836880 and BI 754091 until the MTD is reached or RP2D is determined. For any dose-escalation cohort, at least 3 patients will be required (refer to Section 7). However, in the case that only 2 patients are evaluable and neither has experienced a DLT within the MTD evaluation period, then dose-escalation can occur based on these 2 patients.

Doses may be de-escalated based on the occurrence of DLT and overall safety data. For the first cohort, 3 patients are planned to be treated. A cohort size of at least 3 patients will be treated at each subsequent cohorts. After all patients in a cohort have either experienced a DLT or have been observed for at least the MTD evaluation period without experiencing a DLT, the Bayesian model will be updated with the newly accumulated data. The overdose risk will then be calculated for each dose, and dose escalation will be permitted to all doses which fulfil the EWOC criterion and dose escalation rules according to Section [4.1.3](#). Decision on further recruitment (dose escalation, de-escalation or cohort expansion) will be made by the Safety Monitoring Committee (SMC) based on the collected safety data as well as other data when available. The doses will not exceed the RP2D established in the preceding trials in Western patients.

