If DLTs are observed in the first 2 consecutive patients of a previously untested dose level, subsequent enrolment to that cohort will be stopped. The BLRM will be re-run to confirm that the dose-level still fulfils the EWOC principle. Based on this information, the SMC will evaluate whether the next patients will be enrolled at the same dose level, or if they will be enrolled at a lower dose level.

The SMC may recommend stopping the dose escalation phase after the criterion for MTD ([Section 7.1](#)) is fulfilled. Further patients may be included to confirm this MTD estimate, i.e. to confirm that the EWOC criterion is still fulfilled. If no DLT is observed at a dose of which the efficacy is considered sufficient, the SMC may decide to include an additional number of

patients at the same dose level and/or to declare this dose as the recommended dose for further development (RP2D).

The SMC can declare any dose fulfilling the EWOC criterion as RP2D, independent of the MTD estimate.

BI 836880 and BI 754091 will be administered every 3 weeks. The study treatment can be continued until progressive disease, unacceptable toxicity, or other withdrawal criteria are observed.

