4.1.3 Dose-finding scheme

The dose is planned to be tested in cohorts at pre-defined provisional dose levels. The provisional dose levels to be assigned to different cohorts of patients are listed in [Table 4.1.3:](#)

Proprietary confidential information © 2019 Boehringer Ingelheim International GmbH or one or more of its affiliated companies

1 and 4.1.3: 2. Intermediate or lower dose levels may be investigated if agreed in the SMC, depending on the number of DLTs observed in the trial.

In Part II, increasing doses of BI 836880 will be administered in combination with BI 754091 at 240 mg. The dose of BI 754091 may also be titrated based on DLTs and the overall safety profile of the combination.

Table 4.1.3: 1 Example of dose escalation in Part I*

Dose level	Proposed dose of BI 836880	Increment from previous dose
0	360 mg	Starting dose
1	720 mg*	100%

*Actual dose assignments for a cohort will be communicated separately as determined by the SMC. Intermediate dose level(s) may be investigated depending on the latest DLT rate estimate. Dose levels which are higher than the recommended dose in trial 1336-0001 (720 mg) will not be investigated.

Table 4.1.3: 2 Example of dose escalation in Part II*

Dose level	Proposed dose of BI 836880	Proposed dose of BI 754091	Increment from previous dose (BI 836880)
0	120 mg*	240 mg*	Starting dose
1	360 mg*	240 mg*	200%
2-a	500 mg*	240 mg*	39% (from 360 mg)
2-b	720 mg*	240 mg*	100% (from 360 mg)

*Actual dose assignments for a cohort will be communicated separately as determined by the SMC. Intermediate dose level(s) may be investigated depending on the latest DLT rate estimate. Dose levels which are higher than the recommended dose in trial 1336-0011 will not be investigated. For dose level 2, level 2-a or 2-b will be investigated based on the information from trial 1336-0011.

There will be no dose escalations of BI 836880 or BI 754091 in any one patient.

When the last patient in each cohort completes Cycle 1, the SMC will evaluate the available data. The SMC will review all safety data including, but not limited to, DLTs and all CTCAE Version 5 Grade ≥ 2 toxicity data during cycle 1. Updated safety data on other ongoing patients, including data beyond cycle 1, will be discussed as well. Based on that, a decision on the next dose level to be tested will be made.

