10.5.1 Part I (BI 836880 monotherapy dose finding part)

Hypothetical data scenarios

Hypothetical data scenarios are shown in [Table 10.5.1: 1](#). These scenarios reflect potential on-study data constellations and related escalation as allowed by the model. For each scenario, the probability of overdose for the current dose, as well as the next potential dose and related probabilities of under-dosing, target dose, and over-dosing are shown.

For example, scenario 1 represents the case that no DLT is observed in the first three patients at the starting dose of 360 mg. In this case, the next optimal dose, i.e. the dose with the highest probability of being in the target interval, is 720 mg. Similarly scenario 4 represents the case where no DLTs are observed, and the next optimal dose recommended is 720 mg according to BLRM since no higher dose is available.

Scenarios 5 illustrates the case where low dose cohorts have no DLT and the highest dose level 720 mg/kg has 1 DLT, in such cases, BLRM would continue to assign patients on 720 mg/kg,

In scenario 6, two DLT is observed already in the patient. In this case, the model recommends de-escalation to 360 mg.

Table 10.5.1: 1 Hypothetical data scenarios

Scenario	Dose (mg)	# DLT	# Pat	Current Dose: P(OD)	Next Recommended Dose	Next Dose		
						P(UD)	P(TD)	P(OD)
1	360	0	3	0.005	720	0.728	0.213	0.059
2	360	1	3	0.052	720	0.406	0.416	0.179
3	360	2	3	0.241	360	0.350	0.410	0.241
4	360	0	3					
	720	0	3	0.016	720	0.831	0.152	0.016
5	360	0	3					
	720	1	3	0.093	720	0.561	0.346	0.093

6	360	0	3						
	720	2	3	0.319	360		0.865	0.114	0.021

Operating characteristics

Operating characteristics are a way to assess the long-run behaviour of a model by illustrating the precision of the design in estimating the MTD. Under an assumed true dose-toxicity curve, metrics such as the probability of recommending a dose with true DLT rate in the target interval can be approximated via simulation. [Table 10.5.1: 2](#) describes 5 assumed true dose-toxicity scenarios which were used to assess the operating characteristics of the model. These scenarios reflect a wide range of possible cases as follows:

- Scenario 1: aligned with prior means
- Scenario 2: high-toxicity scenario
- Scenario 3: low-toxicity scenario
- Scenario 4: non-logistic dose-toxicity scenario
- Scenario 5: low-toxicity followed by high-toxicity
- Scenario 6: super high-toxicity scenario

Table 10.5.1: 2 Assumed true dose-toxicity scenarios

Scenario		Dose (mg)	

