		360	720
1 (Prior)	P(DLT)	0.069	0.154
2 (High Tox)		0.321	0.500
3 (Low Tox)		0.039	0.180
4 (Non-Logistic)		0.280	0.360
5 (Low-High)		0.180	0.317
6 (Super High Tox)		0.580	0.769

* Additional dose level 1250mg added (assumed true tox probability of 0.444, 0.603, 0.250, 0.380 and 0.600 under scenarios 1-5 respectively) to allow R code to run. For scenario 6, additional dose level 120mg added (assumed true tox probability of 0.26) to allow R code to run.

For each of these scenarios, 1000 trials were simulated. It was then assessed how often a dose was declared as MTD with true DLT rate in the under-, targeted or over-dose range. Furthermore, the average, minimum and maximum number of patients per trial and the average number of DLTs per trial are reported. Results are shown in [Table 10.5.1: 3](#).

Table 10.5.1: 3 Simulated operating characteristics

Scenario	% of trials declaring an MTD with true DLT rate in				# Patients	# DLT
	underdose	Target dose	Overdose	STOPPED		
1	72.6	0.0	25.7	1.7	11.4(3-24)	2.3(1-8)
2	0.0	40.5	19.3	40.2	8.3(3-27)	3.4(1-10)
3	10.9	88.4	0.0	0.7	11.7(3-33)	1.8(1-6)
4	0.0	29.7	44.9	25.4	9.3(3-24)	3.0(1-12)
5	0.0	83.3	5.3	11.4	10.3(3-21)	3.1(1-8)
6	0.0	46.4	11.6	42.0	8.7(3-18)	4.1(2-9)

In Scenario 1, which reflects the case that the true dose-toxicity is aligned with prior means, 72.6% of the simulated trials declared a dose as MTD with true DLT rate under the targeted dose range, since there is no dose with assumed true toxicity probability in the target interval, therefore it is logical that none of the trials declares a MTD with true tox probability in the target interval. In many cases the model chooses that dose as MTD that is closest to the target interval, this is 720mg with assumed tox probability of 0.154, since 0.154 is very close to the target interval.

Scenario 2 (high-toxicity scenario) shows, that when the true DLT rate is high, i.e. the majority dose levels with true DLT rate above the target interval, 40.5% of the simulated trials declared a dose as MTD with true DLT rate in the targeted dose range. The starting dose has already >32.1% probability of observing at least 2 DLTs out of 3 patients or 1 DLT out of 2 patients in the first cohort. This contributes to the high percentage (40.2%) of all simulated trials for which the trial is stopped, since none of the doses is considered tolerable anymore. This is an expected situation for a high-toxicity scenario.

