Scenarios 3 and 5 show that when the true DLT rate is low and low-high, most of the simulated trials declared a dose as MTD with true DLT rate in the targeted dose range.

Scenario 4 shows, that when the true DLT rate is non-logistic, then more likely the model will declare a overdose as MTD.

Scenario 6 shows that when the true DLT rate is super high, 42% of simulated trials stopped, since none of the doses is considered tolerable anymore. This is an expected situation for a super high-toxicity scenario.

The mean patient numbers range from 8.3 patients (Scenario 2) to 11.7 (Scenario 3) during the simulation. This shows that the planned maximum of 9 patients is reasonable.

In summary, the considered data scenarios show a reasonable behaviour of the model and the operating characteristics demonstrate a good precision of MTD determination.

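### Part I appendix: Table 10.5.1: 1 does not follow from the stated prior (one row crosses the overdose limit), and Table 10.5.1: 3 was simulated with doses outside the planned 360/720 mg

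*Protocol*

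**What the plan says.** Protocol Section 4.1.3 gives 360 mg and 720 mg as the example Part I levels and adds: "Dose levels which are higher than the recommended dose in trial 1336-0001 (720 mg) will not be investigated". Intermediate or lower levels may be used if the SMC agrees. Section 7.1.1 restricts the model's recommendation to doses with less than 25% posterior probability of a DLT rate of 0.33 or more (the EWOC criterion). Table 7.1.1: 2 gives the prior.

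Section 10.5.1 then reports two checks of the design.

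- Table 10.5.1: 1 lists hypothetical data. The text says of them: "These scenarios reflect potential on-study data constellations and related escalation as allowed by the model". Row 3 (2 DLTs in 3 patients at 360 mg) prints P(under/target/over) 0.350/0.410/0.241 and recommends 360 mg again.
- Table 10.5.1: 3 gives operating characteristics from 1000 simulated trials per scenario. The footnote to Table 10.5.1: 2 discloses the extra levels: "Additional dose level 1250mg added (assumed true tox probability of 0.444, 0.603, 0.250, 0.380 and 0.600 under scenarios 1-5 respectively" and "For scenario 6, additional dose level 120mg added (assumed true tox probability of 0.26) to allow R code to run".

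The text reads the results as properties of the design. For Scenario 6 it reports that "42% of simulated trials stopped, since none of the doses is considered tolerable anymore". It takes trial size from the same runs, "The mean patient numbers range from 8.3 patients (Scenario 2) to 11.7 (Scenario 3) during the simulation", and concludes that a maximum of 9 patients is reasonable and that the MTD is determined precisely.

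**The concern.** These two tables are the protocol's only evidence on how the Part I rule behaves. If a row of the first shows a dose passing the overdose limit when the stated model says it fails, the illustration misstates the decision rule at its most safety-relevant point: two DLTs in the first cohort. If the second includes doses that the trial forbids or has not planned, its rates of correct, excessive and stopped outcomes describe another design. The section also disagrees with itself. Its comment on Scenario 2 names at least 2 DLTs in 3 patients at the starting dose as contributing to trials that stop with no tolerable dose, while row 3 of Table 10.5.1: 1 continues at 360 mg after exactly those data.

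**Working it through.** **Inputs.** Section 7.1.1: logit(π_d) = log α + β·log(d/720), θ = (log α, log β), EWOC limit 0.25. Table 7.1.1: 2: component 1 has means (−2.263, 0.116), SDs (0.677, 0.946), correlation −0.076, weight 0.9; component 2 has means (0.405, 1.323), SDs (2, 1), correlation 0, weight 0.1. True rates come from Table 10.5.1: 2 and its footnote.

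**Step 1: reproduce the prior table.** Grid integration gives P(under/target/over):

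- 360 mg: 0.923/0.050/0.027 (Table 7.1.1: 3 prints 0.925/0.049/0.026)
- 720 mg: 0.748/0.171/0.081 (printed 0.751/0.169/0.080)

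So the model and prior are read correctly.

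**Step 2: row 3 of Table 10.5.1: 1.** Each component's weight is multiplied by its marginal likelihood, the integral of π²(1−π) at 360 mg over that component, and rescaled. After 2/3 DLTs the weights move from 0.9/0.1 to 0.544/0.456. At 360 mg, component 1 alone gives 0.661/0.307/0.031 and component 2 alone gives 0.045/0.147/0.808. Then:

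- P(under) = 0.544×0.661 + 0.456×0.045 = 0.380
- P(target) = 0.544×0.307 + 0.456×0.147 = 0.234
- P(over) = 0.544×0.031 + 0.456×0.808 = 0.385 (0.386 before rounding)

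At 720 mg P(over) is 0.50. Neither planned dose is below 0.25. At 120 mg P(over) is 0.121, which passes.

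Several variants were tried: component 1 only (P(over) 0.031), weights left at 0.9/0.1 (0.109), weight 0.95 on component 1 (0.252), other reference doses and wider SDs. None reproduced the printed row together with the printed prior table.

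**Step 3: all rows, P(under/target/over) at the recommended dose.**

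| Row | Printed | Stated prior |
|---|---|---|
| 1 (720 mg) | 0.728/0.213/0.059 | 0.797/0.151/0.051 |
| 2 (720 mg) | 0.406/0.416/0.179 | 0.572/0.298/0.130 |
| 3 (360 mg) | 0.350/0.410/0.241 | 0.380/0.234/0.386 |
| 4 (720 mg) | 0.831/0.152/0.016 | 0.885/0.107/0.007 |
| 5 (720 mg) | 0.561/0.346/0.093 | 0.693/0.252/0.056 |
| 6 (360 mg) | 0.865/0.114/0.021 | 0.867/0.112/0.020 |

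Rows 1 to 5 differ, but only row 3 crosses 0.25.

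**Step 4: which doses produced the MTDs in Table 10.5.1: 3.** This needs only the printed true rates.

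- Scenario 1: 360 and 720 mg have rates 0.069 and 0.154, both below 0.16. All 25.7% overdose MTDs are at 1250 mg (0.444).
- Scenario 5: 360 and 720 mg have 0.180 and 0.317, both in target. All 5.3% overdose MTDs are at 1250 mg (0.600).
- Scenario 6: 360 and 720 mg have 0.580 and 0.769. All 46.4% target MTDs are at 120 mg (0.26).

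The two tables also use different dose sets. For 0/3 at 360 mg and 0/3 at 720 mg, the text to Table 10.5.1: 1 stays at 720 mg for want of a higher dose. On the simulated grid, 1250 mg then has P(over) 0.216, which passes.

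**Step 5: size of the grid effect.** Assumed rules: cohorts of 3 from 360 mg; next dose has the highest P(target) among doses meeting EWOC, at most one level up; stop if none qualifies; declare an MTD with at least 6 patients at the dose and either P(target) above 0.5 or at least 9 patients in total. 1000 trials per scenario; % under/target/over/STOPPED:

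| Scenario | Printed | Re-run, footnote grid | Re-run, 360/720 mg |
|---|---|---|---|
| 1 | 72.6/0.0/25.7/1.7 | 72.4/0/26.2/1.4 | 98.7/0/0/1.3 |
| 2 | 0.0/40.5/19.3/40.2 | 0/37.5/23.3/39.2 | 0/37.2/22.8/40.0 |
| 3 | 10.9/88.4/0.0/0.7 | 10.0/89.7/0/0.3 | 12.8/86.5/0/0.7 |
| 4 | 0.0/29.7/44.9/25.4 | 0/31.4/44.8/23.8 | 0/31.0/44.9/24.1 |
| 5 | 0.0/83.3/5.3/11.4 | 0/82.7/5.4/11.9 | 0/88.5/0/11.5 |
| 6 | 0.0/46.4/11.6/42.0 | 0/52.7/11.1/36.2 | 0/0/8.7/91.3 |

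With 20,000 trials per scenario on the footnote grids, STOPPED is 1.5/40.2/0.5/25.6/11.9/38.8%. A larger run on 360/720 mg gives 89.5% stopped in Scenario 6.

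**Step 6: do the two tables share inputs?** If 2/3 at 360 mg is allowed to pass EWOC, as row 3 prints, STOPPED in Scenarios 2/4/5 becomes 34.1/20.0/7.9%. If it fails, the result is 40.2/25.6/11.9%, against 40.2/25.4/11.4% printed. The simulations therefore look consistent with the stated prior, and Table 10.5.1: 1 does not. The documents do not say why.

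**The case against.** The best defence is that these are appendix illustrations and the added doses are disclosed. Much of that stands, and it limits what may be inferred.

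- **That the SMC would treat more patients at 360 mg because of row 3.** A reader might infer this; the documents do not support it. Section 3.1 has the model updated and the overdose risk recalculated after each cohort, and Section 7.1.1 has the prior for each analysis recorded in the SMC minutes. With the stated prior, a live run after 2/3 would return 0.386 and would not recommend 360 mg.
- **That Scenario 6 is simply invalid.** Section 4.1.3 lets the SMC open lower doses, Section 4.1.6 already uses 120 mg as a reduction dose, and 120 mg passes EWOC after 2/3 at 360 mg. The 90% stopping figure applies only if 120 mg is not opened. What remains is that 120 mg appears in one scenario and not in the other five.
- **That the added doses flatter the design.** In Scenarios 1 and 5, 1250 mg makes it look worse, and STOPPED in Scenarios 1 to 5 barely moves.
- **That the planned size of 9 is thereby shown wrong, or better supported.** Neither follows. The sponsor's stopping rule is not fully stated: under the rule assumed here the largest trial on the footnote grids is 18 patients, against printed maxima up to 33. Differences in trial size therefore mix rule and grid.
- **That the protocol needs a binding enrolment and stopping rule.** Section 3.1 does word its bar around escalation ("it will not be permitted to escalate to a dose which does not fulfil the escalation with overdose control (EWOC) principle"), and after two initial DLTs it leaves the SMC to decide "whether the next patients will be enrolled at the same dose level, or if they will be enrolled at a lower dose level". But the model's recommendation is already confined to EWOC doses, and the SMC may terminate under Section 4.1.4. Discretion above the model is a defensible design choice.

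Disclosure does not answer the main point. The footnote names the added doses, but the text never separates their contribution, and nothing explains row 3.

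**Conclusion.** Two Part I appendix results are wrong as written.

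First, rows 1 to 5 of Table 10.5.1: 1 do not follow from Table 7.1.1: 2. Only row 3 changes a decision: overdose probability 0.386 instead of 0.241 at 360 mg, so no planned dose qualifies. This rests on the printed model and prior alone.

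Second, Table 10.5.1: 3 counts MTDs at a barred dose in Scenarios 1 to 5 and at an unplanned but permissible dose in Scenario 6. Assigning Scenario 1's 25.7%, Scenario 5's 5.3% and Scenario 6's 46.4% to the added doses is certain from the printed true rates. So are the zeros that replace them on 360/720 mg. The figure of about 90% stopped in Scenario 6 depends on the assumed simulation rules, which reproduce that row only roughly on the footnote grid (36.2% and 38.8% in two runs, 42.0% printed).

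This is a correction to the evidence in the appendix. The Section 7.1.1 model, the EWOC limit and the MTD analysis in SAP Section 7.4 stand.

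**What to change.** In protocol Section 10.5.1:

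1. Recompute all six rows of Table 10.5.1: 1 from the Table 7.1.1: 2 prior, or state the prior actually used. In row 3, show that neither 360 nor 720 mg qualifies, and that 120 mg would (P(over) 0.12) if the SMC opens it under Section 4.1.3.
2. Re-run all six scenarios with the sponsor's own stopping rule, written out, on one stated grid with no dose above 720 mg: either 360/720 mg, or 120/360/720 mg throughout. Replace Table 10.5.1: 3 and the footnote.
3. Revise the text that reads from these tables, including the statements on the 9-patient maximum and on the precision of MTD determination, to match the new output.

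The cost is one re-run of existing code, which must accept a grid with no dummy level, and an appendix edit in the next amendment. It adds no patients, visits or data and does not change the escalation rules.

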10.5.2 Part II (BI 836880 and BI 754091 combination dose finding)

Hypothetical data scenarios

Hypothetical data scenarios are shown in [Table 10.5.2: 1](#). These scenarios reflect potential on-study data constellations and related escalation as allowed by the model. For each scenario, the probability of overdose for the current dose combination, as well as the next potential dose combination and related probabilities of under-dosing, target dose, and over-dosing are shown.

Table 10.5.2: 1 Hypothetical data scenarios

Scenario	Dose (mg)	# DLT	# Pat	Current Dose: P(OD)	Next Recommended Dose	Next Dose		
						P(UD)	P(TD)	P(OD)
1	120/240	0	3	0.054	360/240	0.413	0.339	0.248
2	120/240	1	3	0.228	120/240	0.336	0.436	0.228
3	120/240	2	3	0.528	NA	NA	NA	NA
4	120/240	0	3					
	360/240	0	3	0.085	360/240	0.609	0.306	0.085
5	120/240	0	3					
	360/240	1	3	0.295	120/240	0.627	0.324	0.049
6	120/240	0	3					
	360/240	2	3	0.602	120/240	0.408	0.440	0.152

For example, scenario 1 represents the case that no DLT is observed in the first three patients at the starting dose combination of 120/240 mg/kg. In this case, the next optimal dose combination, i.e. the dose combination with the highest probability of being in the target interval, is the next dose combination, i.e., 360/240 mg/kg. Scenarios 5 illustrates the case where low dose combination cohorts have no DLT and the highest dose combination level 360/240 mg/kg has 1 DLT, in such cases, BLM would de-escalate and put patients on 120/240 mg/kg. In scenarios 3, two DLT is observed already in the patient. In this case, the model recommends stopping the trial because of high overdose probabilities.

Operating characteristics

Operating characteristics are a way to assess the long-run behaviour of a model by illustrating the precision of the design in estimating the MTD. Under an assumed true dose-toxicity curve, metrics such as the probability of recommending a dose combination with true DLT rate in the target interval can be approximated via simulation. [Table 10.5.2: 2](#) describes 5 assumed true dose-toxicity scenarios which were used to assess the operating characteristics of the model. These scenarios reflect a wide range of possible cases as follows:

- Scenario 1: aligned with prior means
- Scenario 2: high-toxicity scenario
- Scenario 3: low-toxicity scenario
- Scenario 4: non-logistic dose-toxicity scenario
- Scenario 5: low-toxicity followed by high-toxicity
- Scenario 6: super high-toxicity scenario

Table 10.5.2: 2 Assumed true dose-toxicity scenarios

Scenario		Dose (mg)		
		120/240	360/240	720/240
1 (Prior)	P(DLT)	0.209	0.318	0.680
2 (High Tox)		0.291	0.327	0.516
3 (Low Tox)		0.054	0.128	0.190
4 (Non-Logistic)		0.145	0.290	0.505
5 (Low-High)		0.128	0.169	0.550
6 (Super High Tox)		0.489	0.580	0.769

Table 10.5.2: 3 Simulated operating characteristics

Scenario	% of trials declaring an MTD with true DLT rate in				# Patients	# DLT
	underdose	Target dose	overdose	STOPPED		
1	5.9	76.9	3.8	13.4	11.9 (3-30)	3.3 (1-10)
2	0.0	64.6	9.5	25.9	10.3 (3-30)	3.4 (1-11)
3	68.1	29.2	0.0	2.7	14.6 (3-42)	1.8 (0-8)
4	66.3	7.5	20.8	5.4	11.8 (3-27)	2.8 (1-9)
5	62.2	10.6	23.4	3.8	11.9 (3-27)	2.7 (1-7)

6	0.0	24.4	26.5	49.1	11.0 (3-27)	4.3 (1-10)
---	-----	------	------	------	-------------	------------

In scenario 1, which reflects the case that the true dose-toxicity is aligned with prior means, 76.9% of the simulated trials declared a dose as MTD with true DLT rate in the targeted dose range.

In Scenario 2 (high-toxicity scenario), 64.6% of the simulated trials declared a dose as MTD with true DLT rate in the targeted dose range.

In Scenarios 1 and 2, the starting dose has already >12.0% probability of observing at least 2 DLTs out of 3 patients or 1 DLT out of 2 patients in the first cohort. This contributes to the high percentage of all simulated trials for which the trial is stopped, since none of the doses is considered tolerable anymore. This is an expected situation for assumed dose-toxicity scenarios.

In Scenarios 3-5, there is/are one or two dose(s) with assumed true toxicity probability in the underdosing interval [0.00, 0.16), in some cases the model chooses that dose as MTD that is closest to the target interval, which results in certain percentage of trials with an MTD with true DLT rate in underdosing interval.

Scenario 6 shows that when the true DLT rate is super high, 49.1% of simulated trials stopped, since none of the doses is considered tolerable anymore. This is an expected situation for a super high-toxicity scenario.

The mean patient numbers range from 10.3 patients (Scenario 2) to 14.6 (Scenario 3) during simulation. This shows that the planned maximum of 12 patients is reasonable.

In summary, the considered data scenarios show a reasonable behaviour of the model and the operating characteristics demonstrate a good precision of MTD determination.

